### 4.2 Study Treatment Tolerability

- Table summarizing discontinuations of study-provided drugs within 28 days after study-provided ART and TB treatment initiation by treatment arm [*Safety Criterion #2; see section 1.5.2*].
- Table summarizing discontinuations of study-provided drugs beyond 28 days after study-provided ART and TB treatment initiation by treatment arm.

### 4.3 Diagnoses

- Table summarizing all new, post-baseline diagnoses by treatment arm.
- Table summarizing of all new, post-baseline primary diagnoses of grade 3+ and primary diagnoses that had grade 3+ associated signs, symptoms, and laboratory abnormalities from EVW0206 and EVW0207 forms, by type, with associated signs/symptoms and laboratory abnormalities by treatment arm.

### 4.4 MTB-IRIS

- Table summarizing MTB-IRIS diagnoses with time from TB treatment initiation, grade, and time to resolution, if available, by treatment arm.
- Table summarizing the MTB-IRIS diagnoses, with associated signs/symptoms and laboratory abnormalities by treatment arm.

#### **4.5 Deaths**

- Table summarizing the primary and contributing causes of death with time from study-provided ART and TB medications initiation and attribution to study drug, by treatment arm.

- Table summarizing the reasons why PK samples were not collected strictly within the time frame specified in the protocol by treatment arm.

### 5.1 PK Interim Objectives

#### 5.1.1 Lopinavir (LPV)

- **Note:** The LPV PK interim analysis will be analyzed in Arm B only.

- Table summarizing the number of participants excluded from the LPV interim PK analysis with reasons.
- Table summarizing the number of participants in Arm B whose  $C_{min}$  is  $<1$  mg/L. LPV concentrations in Arm B will be judged acceptable if no more than three participants have a  $C_{min} < 1$  mg/L. [PK Criterion #1; see section 1.5.1].
- Table summarizing the number of participants in Arm B whose  $C_{min}$  is  $<1$  mg/L, including those participants the pharmacologist deemed PK-evaluable (based on the participants' plasma LPV concentrations). LPV concentrations in Arm B will be judged acceptable if no more than three participants have a  $C_{min} < 1$  mg/L. [PK Criterion #1; see section 1.5.1].
- Table of  $C_{min}$  and  $C_{max}$  values for participants meeting the LPV PK criterion of  $C_{min} < 1$  mg/mL.

### 5.1.2 Rifabutin (RBT)

- **Note:** Only Arms A and C will be included.
- Table summarizing the number of participants excluded from the RBT PK interim analysis with reasons by treatment arm.
- Table summarizing the comparison of the RBT AUC and  $C_{max}$  to historical controls (Sekar) with ratios and 90% confidence intervals around the ratios by treatment arm. RBT concentrations in Arms A and C will be judged acceptable if the 90% confidence intervals of the ratios of the RBT concentrations (when co-administered with LPV/r) relative to daily RBT concentrations in the absence of LPV/r are fully contained within the pre-specified NEB of 67%-150%. [PK Criterion #2; see section 1.5.1].
- Table summarizing the comparison of the RBT AUC and  $C_{max}$  pooled over Arms A and C to historical controls (Sekar) with ratios and 90% confidence intervals around the ratios. RBT concentrations in this analysis will be judged acceptable if the 90% confidence interval of the ratio of the RBT concentrations (when co-administered with LPV/r) relative to daily RBT concentrations in the absence of LPV/r is fully contained within the pre-specified NEB of 67%-150%. [PK Criterion #2; see section 1.5.1].
- Table summarizing the comparison of the RBT AUC and  $C_{max}$  pooled over Arms A and C and including those participants the pharmacologist deemed PK-evaluable (based on the participants' plasma RBT concentrations) to historical controls (Sekar) with ratios and 90% confidence intervals around the ratios. RBT concentrations in this analysis will be judged acceptable if the 90% confidence interval of the ratio of the RBT concentrations (when co-administered with LPV/r) relative to daily RBT concentrations in the absence of LPV/r is fully contained within the pre-specified NEB of 67%-150%. [PK Criterion #2; see section 1.5.1].

## 5.2 PK Study Objectives

### 5.2.1 Lopinavir (LPV)

- **Note:** The historical controls are Umeh, Schöller-Gyüre, Ngoc Lan, Naiker, and Matteelli.

- Table summarizing the number of participants excluded from the LPV PK analysis with reasons by treatment arm.
- Table summarizing the LPV PK parameters (all available) with sample size, mean, standard deviation, coefficient of variation, median, and quartiles by treatment arm, with Wilcoxon p-values.
- Table summarizing the LPV PK parameters ( $AUC$ ,  $C_{max}$ ,  $C_{min}$ ,  $C_{last}$ ) with sample size, mean, standard deviation, coefficient of variation, median, and quartiles by Arm B versus pooled Arms A and C, with Wilcoxon p-values [PK Study Objective #1; see section 1.6].
- Figure of A5290 and historical control LPV PK parameters ( $AUC$ ,  $C_{max}$ ,  $C_{min}$ ,  $C_{last}$ ). A5290 data will be pooled over all arms and each historical control will be plotted separately [PK Study Objective #1; see section 1.6].
- Table summarizing the comparison of LPV PK parameters ( $AUC$ ,  $C_{max}$ ,  $C_{min}$ ,  $C_{last}$ ) to historical controls, with Wilcoxon p-values. A5290 data will be pooled over all arms and each historical control will be tested separately [PK Study Objective #1; see section 1.6].

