### PK and Safety Criteria

- For RBT (Arms A and C), equivalence analyses will compare day  $12 \pm 2$  (after initiation of ART) RBT 24-hour AUC and  $C_{max}$  with control data derived from prior PK studies, as determined by whether the 90% confidence intervals of the ratios of the RBT concentrations (when co-administered with LPV/r) relative to daily RBT concentrations in the absence of LPV/r are fully contained within the pre-specified NEB of 67%-150%. RBT concentrations in Arms A and C will be judged acceptable if equivalence is declared according to these PK parameters.
- For LPV in Arm B, the primary PK parameter is the day  $12 \pm 2$  (after initiation of ART)  $C_{min}$  ( $C_{12}$ ), and the acceptable lower limit value is  $\geq 1$  mg/L. LPV concentrations in Arm B will be judged acceptable if no more than three participants have a  $C_{min} < 1$  mg/L.
- No more than three participants in any treatment arm experience a Grade 3 or Grade 4 AE attributable to study-provided medication by 28 days after ART initiation.
- No more than three participants in any treatment arm discontinue study-provided drug(s) for treatment-limiting toxicity or intolerance (such that PK assessments within the day  $12 \pm 2$  (after initiation of ART) window cannot be completed).

The justification behind the RBT PK criterion is given in section 9.4.1. The other three criteria depend on the number of events (i.e., no more than 3). Based on Table 9.2 below, supposing the underlying rate is 10%, with  $X=3$ , there is an 87% chance of the study regimen in a particular arm going forward to accrual period 2.

Table 9.2. Probability (%) of Deciding the Criterion is Acceptable Based on a Range of Underlying Rates

Underlying Rate	Probability of X or Fewer Events in 20 Participants Given the Underlying Toxicity Rate:				
	X=1	X=2	X=3	X=4	X=5
0.05	0.736	0.925	0.984	0.997	0.999
0.10	0.392	0.677	0.867	0.957	0.989
0.15	0.176	0.405	0.648	0.830	0.933
0.20	0.069	0.206	0.411	0.630	0.804
0.25	0.024	0.091	0.225	0.415	0.617

The core team will also examine the LPV concentrations in Arms A and C in order to determine if RBT affects LPV concentrations. Any dose modifications of

LPV in Arms A and C will be the guided by the modifications proposed for Arm B (see Table 5.1 in section 5.1.1).

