### 10.2 Pharmacology Study Design for the Dose-Finding Study in Accrual Period 1 Participants

A5290 is a prospective evaluation in participants undergoing treatment for confirmed or probable TB and who require PI-based ART. The dose-finding study in accrual period 1 participants of A5290 is designed to evaluate two primary questions: 1) Is a RBT dose of 150 mg once daily when given with LPV/r adequate? and 2) Is an LPV/r dose of 800/200 mg BID when given with RIF adequate? Intensive PK evaluations will be performed on day  $12 \pm 2$  (after initiation of ART) of concomitant TB and HIV therapy on all accrual period 1 participants.

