### 1.3 Protocol Overview

A5290 is a prospective, randomized, open-label, phase 2b study comparing three lopinavir/ritonavir (LPV/r)-based antiretroviral (ARV) regimens among participants in high tuberculosis (TB) endemic resource-constrained settings undergoing treatment for TB and HIV and requiring protease inhibitor (PI)-based antiretroviral therapy (ART). A two accrual period design is being used, including a full pharmacokinetic (PK) and safety evaluation to be conducted when 54-60 participants enrolled during accrual period 1 have completed 28 days of ARV treatment and day  $12 \pm 2$  (after initiation of study-provided ART and TB medications) drug levels are available. An early assessment by the team will also be completed when 10-12 participants per arm have completed 28 days of ARV treatment and day  $12 \pm 2$  drug levels are available.

The study population is HIV-infected persons (male or female) at least 18 years of age with documented HIV infection, a clinical diagnosis of probable or confirmed active TB (including extrapulmonary TB) with susceptibility to rifampin (RIF), and who require a PI-based ARV regimen.

471 participants will be randomized in a 1:1:1 ratio to receive either:

- Arm A  
ART: LPV 400 mg/RTV 100 mg twice daily (BID) + two NRTIs.  
Anti-TB therapy: Isoniazid (INH), rifabutin (RBT), ethambutol (EMB), pyrazinamide (PZA), and pyridoxine.  
After completion of TB treatment through week 72: LPV 400mg/RTV 100mg BID + two NRTIs.
- Arm B  
ART: LPV 800 mg/RTV 200 mg BID + two NRTIs.  
Anti-TB therapy: INH, rifampin (RIF), EMB, PZA, and pyridoxine.  
After completion of TB treatment through week 72: LPV 400mg/RTV 100mg BID + two NRTIs.

- Arm C  
ART: LPV 400 mg/RTV 100 mg BID + two NRTIs + raltegravir (RAL) 400 mg BID.  
Anti-TB therapy: INH, RBT, EMB, PZA, and pyridoxine.  
After completion of TB treatment through week 72: LPV 400mg/RTV 100mg BID + two NRTIs + RAL.

Accrual will place in two accrual periods. Accrual period 1 will enroll 60 participants (20/arm) who will undergo an initial dose-finding period before continuing regular study follow-up. Accrual will then be suspended until the last SMC review of the interim PK and safety evaluation has been completed. Accrual period 2 will open and randomize the remaining participants to either three arms (n=411) or to the remaining two arms (n=TBD) and will be monitored by the DSMB.

Each participant will be followed until week 72.

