### **1.6 PK Study Objectives**

Since Accrual Period 2 will not open to enroll participants, the PK objectives outlined in the protocol will also be analyzed at this time.

- 1) To evaluate LPV characteristics (area under the curve [AUC], maximum concentration [ $C_{max}$ ], minimum concentration [ $C_{min}$ ]) in participants enrolled in Arms A, B, and C, accrual periods 1 and 2.
- 2) To evaluate the RBT PK characteristics (AUC,  $C_{max}$ ,  $C_{min}$ ) in participants enrolled in Arms A and C, accrual periods 1 and 2.
- 3) To evaluate RAL PK characteristics (AUC,  $C_{max}$ ,  $C_{min}$ ) in participants enrolled in Arm C, accrual period 2.

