### 5.2.2 Rifabutin (RBT)

- **Note:** The historical controls are Sekar, Ngoc Lan, and Naiker. Only Arms A and C will be included.
- Table summarizing the number of participants excluded from the RBT PK interim analysis with reasons by treatment arm.
- Table summarizing the RBT PK parameters (all available) with sample size, mean, standard deviation, coefficient of variation, median, and quartiles by treatment arm, with Wilcoxon test p-values [PK Study Objective #2; see section 1.6].
- Figure of A5290 and historical control RBT PK parameters ( $AUC$ ,  $C_{max}$ ,  $C_{last}$ ). A5290 data will be pooled over both arms and each historical control will be plotted separately [PK Study Objective #2; see section 1.6].
- Table summarizing the comparison of RBT PK parameters ( $AUC$ ,  $C_{max}$ ,  $C_{last}$ ) to historical controls, with Wilcoxon p-values. A5290 data will be pooled over both arms and each historical control will be tested separately [PK Study Objective #2; see section 1.6].
- Table summarizing the desacetyl RBT PK parameters (all available) with sample size, mean, standard deviation, coefficient of variation, median, and quartiles by treatment arm, with Wilcoxon test p-values [PK Study Objective #2; see section 1.6].
- Figure of A5290 and historical control desRBT PK parameters ( $AUC$ ,  $C_{max}$ ,  $C_{last}$ ). A5290 data will be pooled over both arms and each historical control will be plotted separately [PK Study Objective #2; see section 1.6].
- Table summarizing the comparison of desRBT PK parameters ( $AUC$ ,  $C_{max}$ ,  $C_{last}$ ) to historical controls, with Wilcoxon p-values. A5290 data will be pooled over both arms and each historical control will be tested separately [PK Study Objective #2; see section 1.6].

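### LPV and RTV are compared with historical controls only after pooling all three arms, so neither regimen is formally compared with any control

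*SAP*

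**What the plan says.** SAP 1.3 gives Arm B as "ART: LPV 800 mg/RTV 200 mg BID + two NRTIs" with rifampin. Arms A and C take LPV/r 400/100 mg BID with rifabutin, and Arm C adds raltegravir.

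SAP 5.2.1 plans one figure and one set of Wilcoxon tests of LPV parameters against five historical controls. For the tests, "A5290 data will be pooled over all arms and each historical control will be tested separately", and the figure uses the same pool. SAP 5.2.4 repeats both instructions for RTV with three controls.

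The other planned LPV and RTV outputs are:

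- LPV and RTV summaries by arm, with Wilcoxon p-values and no control in the comparison (5.2.1, 5.2.4).
- For LPV only, a comparison "by Arm B versus pooled Arms A and C, with Wilcoxon p-values" (5.2.1).
- For the interim criterion, "The LPV PK interim analysis will be analyzed in Arm B only" (5.1.1). This counts participants with Cmin below 1 mg/L, again without a control.

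The LPV analyses serve PK Study Objective #1, which begins "To evaluate LPV characteristics (area under the curve [AUC], maximum concentration" (SAP 1.6). The RTV analyses are tied to no listed objective.

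**The concern.** The protocol asks about LPV regimen by regimen. Section 10.2 asks "Is an LPV/r dose of 800/200 mg BID when given with RIF adequate", which concerns Arm B. The PK and Safety Criteria in 9.5.1 say the core team will "examine the LPV concentrations in Arms A and C in order to determine if RBT affects LPV concentrations", which concerns Arms A and C. A sample that is one third double dose with rifampin and two thirds standard dose with rifabutin answers neither question.

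Comparisons inside the trial cannot fill the gap. Every arm takes a rifamycin at the time of PK sampling, so a difference between Arm B and Arms A and C does not show which side departs from LPV/r exposure without that rifamycin. An external control could help, provided each regimen is compared with it separately.

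At stake is how Objective #1 is read. A null pooled test could be taken as reassurance about both regimens when one is low, or when the two lie on opposite sides of the control.

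**Working it through.** **What is compared with what.** The documents give no figure to reproduce, so the check starts from the planned outputs.

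| Output | Arms | Historical control? |
|---|---|---|
| LPV Cmin count (5.1.1) | B | No, fixed 1 mg/L limit |
| LPV and RTV summaries (5.2.1, 5.2.4) | Each arm | No |
| LPV internal test (5.2.1) | B vs A+C | No |
| LPV and RTV control figures and tests (5.2.1, 5.2.4) | A+B+C pooled | Yes |

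The only control comparisons for LPV and RTV are the pooled ones.

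**Dilution.** Let rB and rAC be the geometric mean ratios to control for Arm B and for Arms A and C. With equal arms the pooled ratio is (rB × rAC²)^(1/3):

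- rB = 0.50, rAC = 1: 0.50^(1/3) = 0.79
- rB = 0.50, rAC = 1.41 (√2): (0.50 × 2)^(1/3) = 1.00
- rB = 0.50, rAC = 0.75: (0.50 × 0.5625)^(1/3) = 0.66
- rB = 0.50, rAC = 0.60: (0.50 × 0.36)^(1/3) = 0.56

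**Effect on the test (illustration).** The 18 evaluable per arm comes from protocol 9.4.1. Control size (10, 16, 20, 30), log-SD (0.6, 0.8, 1.0) and the ratios are assumptions. The method was 20,000 lognormal data sets per scenario with a two-sided Wilcoxon rank-sum test at 0.05. Simulation error is about one percentage point or less. The table gives the percentage of data sets with p < 0.05 using 16 controls, at log-SD 0.6 / 0.8 / 1.0.

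| Arm B ratio | A and C ratio | Arm B alone | All arms pooled |
|---|---|---|---|
| 0.50 | 1.00 | 88 / 65 / 46 | 19 / 14 / 11 |
| 0.50 | 1.41 | 88 / 65 / 47 | 2 / 3 / 4 |
| 0.50 | 0.75 | 88 / 66 / 47 | 63 / 42 / 29 |
| 0.50 | 0.60 | 89 / 66 / 46 | 89 / 67 / 48 |
| 0.75 | 0.75 | 26 / 16 / 12 | 37 / 22 / 16 |

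In the second row, Arms A and C tested together against control are detected in 44 / 27 / 19%, so two real departures disappear in the pool. In the last row, A+C alone gives 33 / 20 / 15%, and pooling gains a little.

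For the first row, over 10 to 30 controls, Arm B alone versus pooled is 77–95% versus 14–30% (log-SD 0.6), 52–79% versus 10–20% (0.8) and 36–59% versus 8–14% (1.0).

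A milder departure shows the same pattern. With Arm B at 0.70, Arms A and C equal to control, 20 controls and CVs of 32%, 50% and 70%, Arm B alone is detected in 90 / 59 / 37% and the pool in 22 / 14 / 9% (3,000 runs). The protocol states the 32% CV for rifabutin only; using it for LPV is an assumption.

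**The case against.** **The protocol does not require this test.** Section 10.3 asks for a historical-control comparison for rifabutin only. For LPV in Arm B it sets a fixed Cmin limit, which is analysed in Arm B alone and bears directly on the adequacy question. The 9.5.1 sentence on Arms A and C describes core-team monitoring. This stands, and it limits the weight of the point. But the SAP chose to add control comparisons and tied the LPV ones to Objective #1, so they should be interpretable.

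**The internal Arm B versus A+C test would usually raise the alarm.** It detects the first table row in 97 / 81 / 62% and the second in about 100 / 99 / 93%, more often than Arm B alone against 16 controls. This also stands, for LPV; RTV has no such split. The test cannot say which side departs from control, and in the third row it is weaker (60 / 39 / 27%) than Arm B alone.

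**Spread may be larger and the departure smaller than assumed.** Protocol 2.1 reports a double-dose LPV 12-hour concentration with an IQR of 1.2–7.7 mg/L. If lognormal, the log-SD is ln(7.7/1.2)/1.349 = 1.38. The first row, over 10 to 30 controls, then gives 21–36% for Arm B alone and 7–10% pooled, so for Cmin even the split test would usually miss a halving. The same study found no significant difference in LPV exposure from baseline, and protocol 5.1.1 expects no substantive rifabutin effect on LPV. But that study enrolled nobody with active TB and its authors warned against extrapolating to such patients. Neither source reassures about RTV.

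**The rifabutin precedent is weak.** SAP 5.2.2 says "Only Arms A and C will be included", but Arm B receives no rifabutin, so nothing else was possible. Conceded. The better precedent is the Arm B versus A+C split already in 5.2.1.

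**Matching controls may not exist for Arm B.** The one LPV control described in the protocol (reference 40, section 2.1) gave standard-dose LPV/r with rifabutin, which matches Arms A and C. The regimens and sizes of the others cannot be seen in the available text, and part of the SAP just before 5.1 is missing from it, so this is not counted as a gap. A lack of matches argues for labelling the Arm B comparison, not for pooling Arm B into it.

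**Conclusion.** The point holds. Every LPV and RTV comparison with a historical control pools two different regimens, and no planned output formally compares either regimen with a control. The dilution is arithmetic. Its size depends on the true pattern and on assumed control sizes and spread: severe if only Arm B departs or the two sides move in opposite directions, nil if all arms shift alike. The pattern is not known in advance, and for active TB it is part of what the study is to find out.

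The consequence is limited. The interim criteria, the by-arm summaries and the internal LPV test are untouched, and a reader can set by-arm values beside control values informally. RTV is secondary to LPV here. This is a change that should be made because it is cheap and makes Objective #1 readable. It does not threaten a decision rule.

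**What to change.** In SAP 5.2.1 and 5.2.4, produce each historical-control figure and test separately for Arm B and for Arms A and C combined. State for each control whether it matches on LPV/r dose and on rifamycin. Where no control matches Arm B, label that comparison descriptive. The all-arm pool may stay as a secondary row.

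The cost is SAP wording, extra table rows and figure panels, with no new data. There are two downsides:

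- Each comparison uses about 18 or 36 participants instead of 54, so power falls if all arms shift alike.
- The number of tests doubles. LPV has 4 parameters × 5 controls = 20 and RTV has 4 × 3 = 12, so 32 become 64. Protocol 9.6.3 treats secondary analyses as exploratory, generally without multiplicity adjustment. The results should therefore be reported mainly as estimates with intervals, and p-values read accordingly.

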### 5.2.2 Rifabutin (RBT)

- **Note:** The historical controls are Sekar, Ngoc Lan, and Naiker. Only Arms A and C will be included.
- Table summarizing the number of participants excluded from the RBT PK interim analysis with reasons by treatment arm.
- Table summarizing the RBT PK parameters (all available) with sample size, mean, standard deviation, coefficient of variation, median, and quartiles by treatment arm, with Wilcoxon test p-values [PK Study Objective #2; see section 1.6].
- Figure of A5290 and historical control RBT PK parameters ( $AUC$ ,  $C_{max}$ ,  $C_{last}$ ). A5290 data will be pooled over both arms and each historical control will be plotted separately [PK Study Objective #2; see section 1.6].
- Table summarizing the comparison of RBT PK parameters ( $AUC$ ,  $C_{max}$ ,  $C_{last}$ ) to historical controls, with Wilcoxon p-values. A5290 data will be pooled over both arms and each historical control will be tested separately [PK Study Objective #2; see section 1.6].
- Table summarizing the desacetyl RBT PK parameters (all available) with sample size, mean, standard deviation, coefficient of variation, median, and quartiles by treatment arm, with Wilcoxon test p-values [PK Study Objective #2; see section 1.6].
- Figure of A5290 and historical control desRBT PK parameters ( $AUC$ ,  $C_{max}$ ,  $C_{last}$ ). A5290 data will be pooled over both arms and each historical control will be plotted separately [PK Study Objective #2; see section 1.6].
- Table summarizing the comparison of desRBT PK parameters ( $AUC$ ,  $C_{max}$ ,  $C_{last}$ ) to historical controls, with Wilcoxon p-values. A5290 data will be pooled over both arms and each historical control will be tested separately [PK Study Objective #2; see section 1.6].

### 5.2.3 Raltegravir (RAL)

- **Note:** The historical controls are Rizk and Brainard. Only Arm C will be included.
- Table summarizing the number of participants excluded from the RAL analysis with reasons.
- Table summarizing the RAL PK parameters (all available) with sample size, mean, standard deviation, coefficient of variation, median, and quartiles.
- Figure of A5290 and historical control RAL PK parameters (AUC,  $C_{\max}$ ,  $C_{\text{last}}$ ). Each historical control will be plotted separately [PK Study Objective #3; see section 1.6].
- Table summarizing the comparison of RAL PK parameters (AUC,  $C_{\max}$ ,  $C_{\text{last}}$ ) to historical controls, with Wilcoxon p-values. Each historical control will be tested separately [PK Study Objective #3; see section 1.6].

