Participants who do not have day  $12 \pm 2$  (after initiation of ART) PK samples will not be replaced. Thus, we will enroll 20 participants in each arm, expecting 18 participants in each arm with evaluable PK data. (However, the accrual period 1 PK and safety interim analysis may lead to proposing additional accrual period 1 participants to assure an adequate PK assessment.)

Accrual will be suspended after the last participant is enrolled into the accrual period 1.

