The primary PK characteristics for LPV are:  $C_{max}$ ,  $T_{max}$ ,  $C_{12h}$ ,  $AUC_{0-12}$ , and CL/F. Standard noncompartmental techniques will be used to assess PK parameters. The AUC will be determined using the trapezoidal rule.  $C_{max}$  will be taken as the maximum observed concentration.  $T_{max}$  is the time at which  $C_{max}$  occurs. If more than one  $C_{max}$  and  $T_{max}$  occur in a given profile, the median of these values will be taken. The pre-dose concentration will be taken as the 12-hour post dose concentration, and will be the directly measured value. CL/F will be calculated as  $CL/F = \text{dose}/AUC_{0-12}$ . The elimination half-life is considered a secondary parameter and will be determined using regression analysis when possible.

For RBT (Arms A and C), an equivalence approach will be used to compare RBT AUC and  $C_{max}$  with those of two control datasets from previous PK studies, as described below. This approach will evaluate whether the 90% CIs of the ratios of the RBT + LPV/r relative to daily RBT PK characteristics are fully contained within a specified no effect boundary. A no effect range of 0.67 to 1.50 will be used. Arms A and C will be judged to pass the RBT PK criterion if equivalence is declared.

For LPV in Arm B, the primary PK parameter is the  $C_{min}$  (trough or 12-hour post dose concentration), and the acceptable lower value is  $\geq 1 \text{ mg/L}$ . Arm B will be judged to pass the LPV  $C_{min}$  criterion if no more than three participants have a  $C_{min} < 1 \text{ mg/L}$ .

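### SAP 5.2 compares exposures with historical controls by Wilcoxon p-value alone; a ratio with a 90% CI is needed to show the size and precision of any difference

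*SAP*

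**What the plan says.** SAP 5.2.3 compares RAL AUC, Cmax and Clast "to historical controls, with Wilcoxon p-values", with a separate test for each control, and notes that "Only Arm C will be included". SAP 5.2.1 (LPV) and 5.2.4 (RTV) use the same test for AUC, Cmax, Cmin and Clast, with this rule: "A5290 data will be pooled over all arms and each historical control will be tested separately". SAP 5.2.2 applies it to RBT and desacetyl-RBT, pooled over Arms A and C. Each drug also has a descriptive table of the A5290 data (n, mean, SD, CV, median, quartiles) and a figure showing A5290 beside each control. For LPV there is also a table of Arm B against pooled Arms A and C, again with Wilcoxon p-values.

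SAP 5.1.2 does it differently. RBT AUC and Cmax are compared with one historical control "with ratios and 90% confidence intervals around the ratios by treatment arm" and judged against 67%-150%. Protocol 10.3 sets that boundary for RBT: "A no effect range of 0.67 to 1.50 will be used".

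On numbers, Protocol 9.4.1 enrols 20 per arm, "expecting 18 participants in each arm with evaluable PK data". SAP 1.6 states that accrual period 2 will not open. SAP section 6 says that the summary will discuss the PK study objectives.

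**The concern.** A comparison with a historical control asks how far exposure under co-treatment differs from exposure in a reference setting. The useful answer is a ratio and its uncertainty. A Wilcoxon p-value mixes the size of the difference with sample size and variability. A large p-value can mean similar exposure, or too few participants to tell.

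SAP 5.1.2 shows that the team already has the better tool. It covers only RBT AUC and Cmax against one control. The RBT comparisons with the other two controls, and everything for desacetyl-RBT, LPV, RAL and RTV, carry a p-value only. The population PK work planned for accrual period 2 will not follow, so for RAL these tables are the trial's only formal comparison with outside data.

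**Working it through.** **Inputs.** Evaluable participants: 18 per arm (Protocol 9.4.1), so about 18 for RAL (Arm C) and 3 x 18 = 54 for pooled LPV or RTV. Control sizes are not in the SAP; 18 is assumed. The test level is not stated; two-sided 0.05 is assumed. The only CV that the protocol states for these comparisons is 32%, for RBT AUC (9.4.1). CVs of 50%, 70% and 100% are assumptions to show the range.

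**Formulas.** Data are taken as log-normal with log-scale SD s = sqrt(ln(1 + CV²)), which gives s = 0.312, 0.472, 0.631 and 0.833 at CV 32%, 50%, 70% and 100%. The 90% CI is the ratio divided and multiplied by exp(t x s x sqrt(1/n1 + 1/n2)), with t the 95th percentile on n1 + n2 - 2 degrees of freedom. Wilcoxon results come from 40,000 simulated studies per cell.

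**Reproducing the plan's own figure.** For 18 v 18 at CV 32%, the factor is exp(1.691 x 0.312 x 0.333) = 1.19. At a ratio of 69.9% the CI is 58.6% to 83.4%; Table 9.1 prints 58.7% to 83.2%. The simulated probability of falling within 67%-150% is 95% at -5% and 95% at +5% (Table 9.1: 93% and 94%), and 87% at -10% and 90% at +10% (Table 9.1: 90% and 90%). With 500 simulations behind the table, this agrees.

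**RAL, 18 v 18: share of studies with p>0.05.**

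| True loss | CV 32% | CV 50% | CV 70% | CV 100% |
|---|---|---|---|---|
| 33% | 5% | 34% | 57% | 73% |
| 50% | 0% | 2% | 13% | 35% |

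**What the interval would add.** The 90% CI factors at 18 v 18 are 1.19, 1.31, 1.43 and 1.60 across the four CVs. Take an observed RAL ratio of 0.70 at CV 70%. The CI is 0.70/1.43 = 0.49 to 0.70 x 1.43 = 1.00. The interval shows that a halving is possible; the p-value alone, somewhat above 0.05, would not.

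**LPV and RTV, 54 v 18.** If all arms share the loss, p>0.05 for a 33% loss occurs in about 1%, 16%, 40% and 61% of studies at the four CVs. For a halving it is about 0%, 0%, 3% and 17%.

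For LPV trough the documents do give a spread. Protocol 2.1 (the section on rifamycins and PI-based regimens) reports a median of 3.7 mg/L and IQR 1.2-7.7 on double-dose LPV/r with RIF. If log-normal, s = ln(7.7/1.2)/(2 x 0.6745) = 1.859/1.349 = 1.38. With that spread in both groups, a halved trough gives p>0.05 in about 58% of studies.

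**Pooling.** If Arm B alone were halved and Arms A and C matched the control, the pooled 54 v 18 test gives p>0.05 in about 55% of studies at CV 32%, 71% at CV 50% and 80% at CV 70%.

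**Why not a pass/fail rule.** With a true ratio of 1.0 and 18 v 18, the chance that the 90% CI lies within 67%-150% is 97%, 61%, 19% and 1% across the four CVs. The boundary was sized for RBT at CV 32% and would often fail a drug with truly unchanged exposure if its CV were higher.

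**The case against.** A reader might infer that, for RAL, LPV and RTV alike, about 18 per group means that a large loss of exposure will be reported as no difference. The documents do not support that.

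- About 18 applies to RAL only. LPV and RTV are pooled to about 54 before the control comparison.
- At the one stated CV (32%, for RBT), a 33% loss in RAL is missed in about 5% of studies and a halving essentially never. A 25% loss would be missed more often, but a ratio of 0.75 lies inside the 0.67 to 1.50 range that the protocol treats as no effect for RBT.
- Nothing in the SAP says that p>0.05 will be read as similar exposure. Section 6 reserves the word acceptable for the section 1.5 criteria and says only that the PK objectives will be discussed. Those objectives are to evaluate PK characteristics.
- Magnitude is not wholly absent. The descriptive tables and figures would show a gross difference, and the table of Arm B against A and C could expose an Arm B deficit in LPV.
- No decision turns on these tables. LPV adequacy in Arm B has its own rule (no more than three participants with Cmin below 1 mg/L), RBT has its interval criterion, and accrual period 2 will not open.

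All of this stands and limits the point to reporting and interpretation. It does not supply what is missing. No planned output in SAP 5.2 gives a difference from a control with its uncertainty, and the SAP names no other basis for conclusions from these comparisons. The larger n for LPV and RTV is gained by combining regimens with different LPV/r doses and rifamycins, so it does not settle the matter for either drug.

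**Conclusion.** The point holds as a fault in the choice of output. The p-value is the only inference against historical controls in SAP 5.2, and it cannot show how large or how certain an exposure difference is.

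The size depends on variability. For RAL, a 33% loss goes undetected in about a third of studies at CV 50% and over half at CV 70%. A halving is missed often only near CV 100%. For LPV trough, the protocol's own quoted spread implies that a halving would be missed in more than half of studies even after pooling. Pooling can separately mask a loss confined to Arm B.

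These figures assume log-normal data, equal spread in both groups, 18 controls and a two-sided 0.05 level; the CVs for RAL and RTV are assumed. The LPV figure applies a spread seen on double-dose LPV/r with RIF to all arms and controls. The log-normal fit to it is approximate: sqrt(1.2 x 7.7) = 3.0 against a reported median of 3.7.

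The documents do not show that the sponsor intends to read non-significance as equivalence, or that any dosing decision rests on these tests.

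**What to change.** In SAP 5.2.1, 5.2.3 and 5.2.4, and for RBT and desacetyl-RBT in 5.2.2, add the geometric mean ratio with 90% CI against each historical control, for AUC, Cmax and Cmin or Clast as listed for each drug. For LPV and RTV, give it by arm, or for Arm B and for pooled Arms A and C separately. One ratio over all arms would average different regimens and be hard to interpret.

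State that the interval is an estimate, that the 67%-150% boundary is not applied as a pass/fail rule outside the RBT criterion, and that a non-significant p-value is not read as similar exposure. Base the section 6 discussion on the intervals. The Wilcoxon p-values may stay as a supplement.

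The cost is a few columns, plus extra rows for LPV and RTV. A two-sample Wilcoxon test already needs subject-level control values. The SAP does not say that these are held; if only published summaries exist for a control, a geometric mean with its CV is enough for the ratio and interval. Some intervals will be wide, which is itself information that the p-value conceals.
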